Using Twitter to Enhance the Social Support of Hispanic and Black Dementia Caregivers

NCT03865498

IRB approved on 09/13/2021

Study Description

1. Study Purpose and Rationale

The purpose of this study is to evaluate the impact of the Twitter-based intervention on Tweet content and social network structures of Hispanic and Black dementia caregiver networks. The prevalence of dementia is higher in Hispanics and Blacks than non-Hispanic Whites.^{1, 2} Moreover, the caregiving demands in dementia exceed that of other chronic conditions.^{3, 4} Consequently, dementia caregivers often experience social isolation and loneliness and decreased health status, and lower quality of life.⁵⁻⁸ Social support interventions have been demonstrated to help mitigate these issues.^{5, 9} The expansion of social media use, particularly Twitter, among Hispanics and Blacks, ¹⁰⁻¹⁵ offers great promise for improving social support for Hispanic and Black dementia caregivers.¹⁶ In addition, the availability of large volumes of Tweets and associated metadata make it possible to apply innovative data science methods to characterize engagement in a social support intervention and to assess its efficacy over time.¹⁷⁻²⁷ However, analytic frameworks for analyzing content and social network structures in Twitter communities are relatively new and evolving rapidly, and there has been limited use of Twitter for intervention delivery.¹⁶

Our research team has conducted federally-funded research with Twitter data since 2009 and published a practical tutorial on Twitter mining in the *American Journal of Preventive Medicine* in 2013.²⁵ More recently, through the New York City Hispanic Dementia Caregiver Research Program (R01 NR014430) and a supplement (R01 NR014430-03S2) which focused on understanding mechanisms of social support in Twitter, we have developed a Tweet corpus of >2.6 million English and Spanish Tweets related to dementia caregiving. Moreover, we have applied data science-based cultural analytic techniques for Twitter data mining and developed innovation visualizations for Twitter data.^{17, 19-27} Analyses of Tweet topics detected a high frequency of social support topics and revealed that the sentiments of Hispanic dementia caregivers were primarily negative.^{17, 19-21, 24} Network analyses revealed a high proportion of isolates (i.e., Tweets without responses) and a low proportion of balanced micro-networks, suggesting sub-optimal social support in the networks.^{17-22, 24} We also created a database of >1600 online resources for dementia caregiving.^{17-22, 24} This substantial preliminary work provides evidence that our research team is uniquely qualified to operationalize, implement, and evaluate a Twitter-based social support intervention for Hispanic and Black dementia caregivers.¹⁷⁻³¹

2. Study Design and Statistical Procedures

Design: The study purpose will be achieved through a quasi-experimental design (non-equivalent 2 group pre and post-test design). The intervention group is **anonymous followers** of two Twitter accounts established: the African American/Black dementia caregiver group and the Hispanic dementia caregiver group. **No personally identifiable information (PII)** under the definition used by the National Institute of Standards and Technology (NIST) such as names, addresses, date of birth, and email addresses will be collected. Instead, we will analyze publicly available Tweet data for network engagement (count of pressing 'like,' 'retweet,' 'reply' button), emotional valence (auto-calculation from Tweet text messages: "this is so helpful"-emotion score +4, "I face many challenges"- emotion score -6), topic changes, the volume of isolates, size and number of communities, and communication types for our outcome variables. To examine general confounders, **three demographic elements (self-reported age, gender, race/ethnicity, un-linkable to name, phone, email, or address)**.

The intervention is summarized in table 1 and comprises the posting of one Tweet per day, replying or directly messaging followers, liking someone else's Tweet, retweeting someone else's Tweet, and a monthly Twitter chat at an established time. The Tweet messages which the IRB will approve from our Aim 2 will be used as an intervention. In addition, Twitter who re-confirm Twitter terms of the agreement, including privacy policy and terms of service (Appendix attached), will be required for this study. If someone decides to follow one of our accounts (i.e., participate in the intervention) and subsequently changes their mind, they can easily change stop following our networks. We will retain our de-identified Twitter followers for our Twitter communities in multiple ways: 1) we will invite caregivers in the dementia caregiver registries (including the NHiRP project), who agreed to be contacted for the future study, developed by Drs. [name] and [name] to follow the relevant Twitter accounts; 2) we will use online advertising function for marketing our Twitter communities using TwitterAds (15 days in Year 3 and 15 days in Year 4); 3) research flyers will be posted in relevant clinics; 4) we will send an invitation via Twitter to the publicly available user IDs (estimated Black user

IDs-2500, estimated Hispanic user IDs-1800); 4) using the @mention function, we will ask the existing organization and community leaders (e.g., @alzassociation, which has 107K followers) to retweet our invitation messages to reach out their followers; and 5) monthly, we will determine if there are any new key dementia/Alzheimer's Twitter community leaders and send out an invitation to the publicly available user I.D.s.

Table 1. Twitter-based Intervention

Concepts	Tweets	Time	Source	Function	Recipient
Instrumental support	Prepackaged	Daily**	library	Post*	All followers
Appraisal support	Prepackaged	Daily**	library	Post*	All followers
Informational support	Prepackaged	Daily**	library	Post*	All followers
Emotional support	Prepackaged	Daily**	library	Post*	All followers
Engage in social network	Participate in discussion	Daily	Tweeters	Reply,	All followers
				Direct message	(Individual)
Engage in social network	Answer questions from a direct message	Daily	Tweeters	Direct message	An individual
Engage in social network	Answer question from a posted message	Daily	Tweeters	Reply	All followers
Engage in social network	Like followers' Tweets	Daily	Tweeters	Like	All followers
Engage in social network	Retweet relevant Tweets	Daily	Tweeters	Retweet	All followers
Social support	Host 2hr Twitter chat	Monthly	experts	#hashtag	All followers

*posting: open to all followers. **a message daily (e.g., Monday: Instrumental, Tuesday: Emotional, Wednesday: Informational, Thursday: Appraisal, Friday: Instrumental, repeat the sequence to avoid weekday and weekend effect.

The setting, Sample, and Power Analysis: The setting is the U.S. The Sample will be the de-identified flowers of one of the two dementia caregiver networks (Hispanic, Black). Given our recruitment strategies and preliminary work, we anticipate recruiting > 400 de-identified followers in each group. Based on similar Twitter communities (e.g., @ dementiatoday), population N is estimated at 153,300 for 365 days.

For statistical analyses, the necessary sample sizes for hypothesis 1 and hypothesis 2 based upon the power analysis³⁴ are described below. Hypothesis 1 focuses on within-group differences and Hypothesis 2 on between-group differences. The hypotheses include both continuous (emotion valence) and binary (% of isolates) outcome variables.

Hypothesis 1: Assuming a correlation of pre- and post-test conservatively: reliability of 300 followers will be required. If the correlation between pre- and post is larger, smaller sample sizes are required. Thus, a sample of 300 Blacks and 300 Hispanics is adequate to examine the within-subject change using a paired t-test. The pre-post-test for binary outcomes (% of isolates) is McNemar's test. The minimum required sample size is 208. Thus, the proposed sample sizes will be adequate to test within-group differences.

Hypothesis 2: The total minimum required sample size in each ethnic group (Black and Hispanic) will be 192 for a total of 385 with effect size 0.332 (Cohen's d). Assuming that α =0.05, 1- β =0.80 (power), the total minimum required sample size for the two groups (Black and Hispanic) with effect size 0.1525 (P_0 - P_1) is **318** (**159 per group**).

Data analysis: Extensive processing is required before the actual data analysis, which comprises data science methods and statistical tests for our hypotheses.

Data processing: We will process Twitter data for data analyses through several steps:1) merging of data files in our institutional high performance computing (HPC) environment (Habanero), 2) converting XML to txt file format into a human-readable format for integrity checking, 3) feature selection, and 4) indexing.³⁵

Data science analyses for publicly available de-identified data: We will use a variety of software packages (R, Python, Nvivo, ORA, NodeXL, SAS) for the data science analyses. Since Twitter user demographics and personal data are not directly available, we will apply algorithms to users' Tweets and images to estimate their demographics, including those considered Social Determinants of Health.³⁶⁻³⁹ We will stratify those variables into categories for data analysis procedures as relevant. To answer research question 1, we will descriptively characterize (e.g., #Tweets, # followers, #likes, #retweets) Twitter activity in the two networks. To address the second research question, we will apply Syuzhet sentiment analysis and LDA to characterize negative affect scores and topic models, respectively. For the third research question, we will compute the network measures listed in **Table 1**.

Emotional valence, expressing topics, and conversational styles in macro-,meso- and micro-level among de-identified Twitter followers will be computed from publicly available Tweet data. Unlike the traditional methods, data science methods such as natural language processing (NLP) and network analyses enable us to detect emotional valence score, changes in topics, volume of isolates, and communication styles without asking the users any questionnaires. The following table summarizes concepts, measurements, units of analysis, and data science analytic methods.

Table 1. Concepts, Measures, Data Science Methods and Units of Analysis

	Concept	Measures [§]	Data Science Methods	Unit
Content	Emotional valence ⁴⁰	Emotional valence score ^{18, 40-45} detected from text data (e.g., "This is so helpful" – emotion score +4, "I am sad"- emotion score -6)	Syuzhet packages 46	***
	Social support (informational, instrumental, emotional, appraisal)	Topic changes in social support ^{17, 19-21}	Topic modeling using hierarchical ⁵¹ and n-gram embedded LDA algorithms ⁵¹⁻⁵⁴	***
ø)	Social network: Macro- level ⁵⁵	The volume of isolates, Network type, Density, Centralization, Cohesiveness 26, 27, 55, 56	Network analysis ¹⁷⁻ 20, 23, 24, 26, 27	***
Structure	Social network: Meso- level ^{57, 58}	Size and number of communities, the volume of the community activities, leaders of community ^{26, 27, 56, 57}	Clauset-Newman- Moore ⁵⁹ Girvan-Newman ⁵⁸	**
	Social network: Micro- level ⁶⁰	16 communication types among triad, number of individual posting activities 26, 27, 56, 57, 60	Triad census analysis ⁶⁰	*

^{*} individual level, ** community level, *** global network level, §all measures in real-time)

Statistical Analyses: Pre-post comparisons will be examined from baseline (3 months pre-intervention) to 3 months (9-12) months after initiation of the intervention. Analyses of pre-post mean differences will be performed using SAS PROC TTEST, PROC Mixed, PROC GLIMMIX, and PROC CATMOD, with adjustments for the correlation within participants induced by repeated measures and for unreliability and missing data treatment. The continuous outcome will be analyzed using SAS PROC TTEST, PROC Mixed, and the binary outcome will

be analyzed using PROC GLIMMIX or PROC CATMOD (for the McNemar test), depending on the missing data. We will compare measures among the two groups using independent t-tests for continuous variables and Chisquare tests for proportions to test the second hypothesis. Machine learning-based trend analysis 61, 62 will be applied for the continuously detected emotional valence score.

[figure not shown]
3. Study Procedures

Procedure: Publicly available Tweet data (e.g., Tweets, time stamp, self-reported location) from de-identified Twitter followers of our Twitter sites will be obtained from the public database. No personally identifiable information (PII) under the definition used by the National Institute of Standards and Technology (NIST) such as names, addresses, date of birth, and email addresses will be collected. We will analyze publicly available Tweet data for emotional valence (auto-estimation from Tweet messages), topic changes, the volume of isolates, size and number of communities, and communication types for our outcome variables. In addition, three demographic elements (i.e., self-reported age, gender, race/ethnicity, which are un-linkable to their PIIs) will be collected to examine general confounders. Again, no PII will be used or accessed.

Intervention: Two Tweeters, including a bilingual Hispanic, will strictly follow the intervention delivery protocol developed in Aim 2 with guidance from the Tweet-S2 Expert Panel. Daily for 365 days that cross Years 3 and 4, the Tweeters will post a Tweet from the Tweet library to each Twitter community alternating among those related to information, instrumental, emotional, and appraisal support. The Tweeter will also engage in social network activities by replying to, liking, and retweeting messages posted by others. This intervention will be consistently conducted (e.g., time, center brand themes, designs) to enhance intervention fidelity.⁶³ After a Tweet is posted, followers can respond using Twitter functions (e.g., retweet to quote and disseminate our Tweet message, posting a Tweet message to express their after thoughts and questions using @mention, like. and reply function). In addition, the P.I. will examine the archive files to monitor intervention fidelity and reinforce expected behaviors of the Tweeters as needed.

Publicly available Twitter data collection: During the baseline (3 months pre-intervention) and intervention (365 days crossing Years 3 and 4) periods, we will collect publicly available Tweet messages and associated metadata (e.g., userID, relationship, time stamp, Tweet, Hashtags, Twitter page, geo code, location, type) daily. We will also double-check the data integrity (e.g., incompletely captured data) daily. In terms of missing Twitter data,⁶⁴ we will make an effort to minimize missing data in 3 ways: our designated Tweeters and the P.I. will be available during data collection, two collection tools (NodeXL and NCapture) will be used, and collection of Tweets will be monitored daily to ensure that capture was adequate and with no PII. Figure 1 shows an example of publicly available data collected.

Figure 1. An example of publicly available data collected via NodeXL: Vertex 1 and 2 will be used for macro, meso, and micro level network analyses. Tweet text with no personal identifiers will be used for text analyses, including emotion score calculation and topic modeling.

upon following Twitter networks

will be strictly prohibited and daily monitored/removed.

4. Study Drugs or Devices

Not applicable

5. Study Instruments (e.g., Questionnaires, Interview Outlines, Focus Group Guides) **No direct instrumentations** such as questionnaires (i.e., survey, interview) will be applied for the outcome measurers. Instead, emotional valence, topics, and conversational styles in macro-,meso- and micro-level among **anonymous Twitter followers** will be computed from the publicly available Tweet data. Unlike the traditional methods, data science methods such as natural language processing (NLP) and network analyses enable us to detect emotional valence score, changes in topics, volume of isolates, and communication styles without asking the users. Table 1 above in Data Analyses summarizes concepts, measurements, units of analysis, and data science analytic methods.

6. Study Subjects

Inclusion criteria: The anonymous dementia caregivers must be 18 years of age or older, Black or Hispanic, living in the U.S. including the U.S. territories, a dementia caregiver with any duration, able to speak English or Spanish/bilingual. The participants must agree to terms of conditions of use and privacy policy and rules of one of the two dementia caregiver networks (Hispanic and Black), the Twitter user agreement of the terms of service, Twitter privacy policy, and Twitter rules, including intellectual property, violence, misconduct, abusive behavior, private information and spam and security, and use a smartphone or a feature phone (i.e., a cell phone with text messaging).

Screening/Determining Eligibility

Upon a Twitter user follows one of our Twitter networks after seeing our advertisement on Twitter or our flyers from our clinics and emails, our team will automatically receive a new follower notification from Twitter. Within 24 hours during the weekdays (72 hours during the weekend), our Tweeter/coordinator will send a screening message via the direct message function in Twitter (script attached) and respond if they are eligible to participate in our research Twitter networks (script attached).

When a Twitter user meets our inclusion criteria, the study staff will remind the user regarding our Twitter networks as a research study, voluntary participation, and unfollowing our Twitter networking sites at any time. Furthermore, using the direct message function via Twitter, our study staffs will ensure that the eligible user 1) creates an anonymous Twitter handle if the person uses his/her full name as a Twitter handle, and 2) hides their names from the profile setting. When a Twitter user does not meet our inclusion criteria, our study staff will request them unfollowing our Twitter network via a direct message function (script attached). Ineligible followers will be blocked within 72 hours after the unfollowing request.

7. Recruitment

Considering 60% attrition rate of anonymous online users, we anticipate to enroll >400 per group, to accrue up to a total of 800 (400 per group, total minimum required Sample are 318 users: 159 per group) and retain anonymous followers (no actual name or phone number/email address on the profile or Twitter handle) for our Twitter communities in multiple ways: 1) A flyer will be distributed up to 5 times (per a week) via an email to the caregivers, who agreed to be contacted for the future studies, in the dementia caregiver registries; 2) we will use an online advertising function for marketing our Twitter communities using TwitterAds (15 days in Year 3 and 15 days in Year 4); 3) research flyers will be posted in relevant clinics (i.e., AIM clinic and neurology units at CUIMC); 4) using the @mention function, we will ask the community leaders (e.g., @alzassociation, which has 107K followers) to post our flyer; and 5) every month, we will contact relevant community leaders within Twitter to post our flyer. This study does not offer any incentives (e.g., no online credits, no monetary compensation).

8. Informed Consent with waiver of documentation (45 CFR 46.116)

Informed consent will be obtained with a waiver of documentation (e.g., signature). Anonymous Twitter users without PII (no name, email address, phone number, or addresses are linkable) will participate in this study, analyzing publicly available de-identified data. Accidental PII exposure will be strictly prohibited (see four strategies in privacy protection) and monitored daily. Therefore, this research to post social

support messages to our Twitter network followers involves minimal risk to the subject. The signature on the informed consent document would be the only record linking the subject to the research.

9. Confidentiality of Study Data

Our study data will comprise 1) publicly available Twitter data and 2) three demographic elements, including self-reported age, gender, and race/ethnicity (un-linkable to name, email address, phone number). For both, our team strictly follows the institutional policy for computers and endpoint devices to store the Tweet corpora. Data preprocessing and manipulation will occur using the secure data repositories at the Columbia University Medical Center, such that no data we collect will be stored out of our control. We will use a secured network for the Department of General Medicine for temporary storage for daily data collection, as well as a university-provided fully encrypted external drive for the long term backup purpose. Although our Twitter data does not contain personally identifiable information, all data will be managed and stored under our institutional policy which all endpoint devices of our research team should be protected with 256-bit encryption (at minimum), which severely restricts access to the data in a far superior manner than password protection. For data sharing and preparation, we will use a passcode-protected Columbia University Habanero HPC environment for the transient file storage while merging, converting, and computing the large volume of data

10. Privacy Protections

The anonymous followers of our Twitter sites will be informed that no identifiers such as names or email addresses will be stored in the data collection. Their PII, such as email addresses and names if the participants contacted the study team via email for the recruitment purpose, will be removed from the recruitment documentation on the day of data collection. All data will be de-identified before analysis, and no identifying information about the individual will be used in reporting the study results. We will implement the following protections against risks:

- 1) Warning: our two dementia caregiver Twitter networks will have a privacy protection reminder with a warning sign on their title pages. Our Twitter network sites will include short and relevant privacy statements (i.e., sharing aggregate data of age group and estimated gender, how to contact our organization's data protection officer.)
- 2) Reminding: a designated research team member will post a welcome video reminding the target audience about the protection of privacy using a Tweet direct message function upon a participant following (subscribing) our Twitter sites and post a reminder Tweet about privacy protection once a week (i.e., Posting self-identifiable photos, names, email address or phone number will be strictly prohibited).
- 3) Monitoring Privacy: a designated research team member will monitor user-generated content daily for the risks of exposure to PII.
- 4) Monitoring Content: A designated research team member will remove Misleading or inappropriate content as necessary daily.

11. Potential Risks

There are some minimal risks specific to this study. First, though we will not collect any direct PIIs nor personally identifying photographic images, and all analyses are done at an aggregate level, followers (i.e., site users/study participants) may accidentally post texts or images that contain PII. Second, there is a possibility that followers may post information that is inaccurate and potentially harmful.

12. Potential benefits of the proposed research to the subjects and others

Those who participate in the Twitter-based intervention study may perceived increased social support (informational, instrumental, emotional, appraisal) and may feel belongingness which is a human basic need.

13. Importance of the knowledge to be gained

The important contributions of this study to knowledge development are both substantive and methodological. The study will extend what is known about dementia caregiving in minority populations and the mechanisms of social support. Moreover, the study will expand what is known about using Twitter as a mode for intervention delivery and methods for creating culture-specific lexica and culturally-sensitive Tweet messages and analysis of Twitter data.

14. Alternatives

This research involves an intervention that presents no greater than minimal risk to participants. If participants change their minds, they can easily change a setting to stop following our Twitter networks.

15. Data and Safety Monitoring

Although our Tweet corpora only include publicly available Twitter data, our team strictly follows the institutional policy for computers and endpoint devices to store the Tweet corpora. Data preprocessing and manipulation will occur using the secure data repositories at the Columbia University Irving Medical Center. No data we collect will be stored out of our control. We will use a secured network for the General Medicine for temporary storage for daily data collection, as well as a university-provided fully encrypted laptop and a university-provided fully encrypted external drive for the long term backup purpose. Although our Twitter data does not contain personally identifiable information, all data will be managed and stored under our institutional policy which all endpoint devices of our research team should be protected with 256-bit encryption (at minimum), which severely restricts access to the data in a far superior manner than password protection. For data sharing and preparation, we will use a passcode-protected Columbia University Terremoto HPC environment for the transient file storage while merging, converting, and computing the large volume of data,

References

- 2. 2016 Alzheimer's disease facts and figures. *Alzheimer's & Dementia: The Journal of the Alzheimer's Association*.12:459-509
- 3. National Alliance for Caregiving. Dementia caregiving in the u.S. Available at http://www.Caregiving.Org/wp-content/uploads/2017/02/dementiacaregivingfinal_web.Pdf. 2017 Feb
- 5. Dam AE, de Vugt ME, Klinkenberg IP, Verhey FR, van Boxtel MP. A systematic review of social support interventions for caregivers of people with dementia: Are they doing what they promise? *Maturitas*. 2016;85:117-130
- 6. Sarkar S. Impact of caregiving role in the quality of life of family caregivers for persons with Alzheimer's disease. 2015

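### The isolate outcome is defined on Tweets but tested with McNemar's test on followers; if follower status means that no Tweet was answered, it is confounded by posting volume

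*Combined protocol and SAP*

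**What the plan says.** Section 1 (Study Purpose and Rationale) gives the only definition, in describing earlier work: "Network analyses revealed a high proportion of isolates (i.e., Tweets without responses". It reads a high proportion as a sign of weak support in the network.

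Section 2, in the table of concepts, measures and units, lists "The volume of isolates, Network type, Density, Centralization, Cohesiveness" as macro-level measures. Their unit mark is explained in the footnote as "global network level".

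Section 2, Hypothesis 1, counts its sample in followers and treats the change as within-person: "a sample of 300 Blacks and 300 Hispanics is adequate to examine the within-subject change using a paired t-test". For the percentage of isolates it says "The pre-post-test for binary outcomes (% of isolates) is McNemar's test", followed by "The minimum required sample size is 208". No effect size, discordant proportion, alpha or power is attached to that number.

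Section 2, Statistical Analyses, pairs the data by person, with "adjustments for the correlation within participants induced by repeated measures". It says the binary outcome will "be analyzed using PROC GLIMMIX or PROC CATMOD (for the McNemar test), depending on the missing data". The windows are the three months before the intervention and months 9 to 12 after it starts.

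**The concern.** Three units are in play: the Tweet (definition), the network (measures table) and the follower (test and sample size). A paired binary test on followers requires every Tweet a follower wrote in a window to be reduced to one yes/no. The plan gives no rule for this, and none for a follower who wrote nothing.

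The rule matters because the number of Tweets is unlikely to stay constant. Followers receive a daily post and a monthly chat, and they are expected to react by replying and posting. Under the natural rule that an isolate is a follower with no answered Tweet, more Tweets mean more chances of one answer. A significant fall in isolates could then be reported as better support although each Tweet is as likely as before to go unanswered. Both groups receive the intervention, so no untreated group would expose the artefact.

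**Working it through.** **1. The plan's figure of 208.** The usual normal approximation for McNemar's test is n = [1.96·√pd + 0.842·√(pd − d²)]² / d², where pd is the discordant proportion and d the net change (two-sided 0.05, 80% power). The plan gives neither pd nor d. With d = 0.10 and pd = 0.268: (1.96 × 0.5177 + 0.842 × 0.5079)² / 0.01 = 1.442² / 0.01 ≈ 208. The pairs d = 0.12, pd = 0.386 and d = 0.1525, pd = 0.623 also return 208. The figure can be neither confirmed nor refuted.

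**2. Inputs for the mechanism.**
- Followers: 400 per group with 60% attrition (Section 7) leaves 400 × 0.40 = 160, taking attrition to apply to the enrolled 400. The stated 208 is used as well.
- q, the chance that a Tweet is answered: not given. Assumed 5% or 10%, the same in both windows.
- m, Tweets per follower per window: not given. Assumed 2 rising to 3, or 10 rising to 15 (both 1.5-fold), with 10 rising to 12 as a milder case.

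**3. Follower status under the rule that no Tweet is answered.** P(isolate) = (1 − q)^m. With independent windows, the discordant cells are b = p1(1 − p2) and c = p2(1 − p1). McNemar's test (chi-square above 3.84) was simulated.

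| q | m, pre to post | Isolates, pre to post | Drop (points) | Rejection, n = 160 |
|---|---|---|---|---|
| 5% | 2 to 3 | 90.3% to 85.7% | 4.5 | 23% |
| 10% | 2 to 3 | 81.0% to 72.9% | 8.1 | 40% |
| 10% | 10 to 12 | 34.9% to 28.2% | 6.6 | 25% |
| 5% | 10 to 15 | 59.9% to 46.3% | 13.5 | 68% |
| 10% | 10 to 15 | 34.9% to 20.6% | 14.3 | 81–82% |

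In the last row b = 0.349 × 0.794 = 0.277 and c = 0.206 × 0.651 = 0.134. With 208 followers, rejection there is 90–91%.

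**4. The per-Tweet quantity.** The proportion of unanswered Tweets is 1 − q in both windows, so it does not move. In the last row's scenario a paired test on each follower's proportion rejects in about 5% of samples, as it should.

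**5. Relaxing the assumptions.** Letting followers differ in q, and letting each follower's q vary between windows, lowers the last row at n = 160 to about 44–64%. The artefact shrinks but remains.

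**6. Other collapsing rules.** If an isolate is a follower with at least one unanswered Tweet, P = 1 − q^m, which rises with m. With q of 10% to 30% and a mean of 3 or 5 Tweets, doubling the posts raises it by 0.017 to 0.086. Under a rule that most Tweets are unanswered, the rise is 0.034 to 0.084. At q = 10% and 10 Tweets or more, 1 − q^m is already above 0.9999 and cannot move.

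**7. Non-posters.** With m = 0, (1 − q)^0 = 1: a silent follower counts as an isolate if the rule is applied literally, or drops out if a Tweet is required. The plan does not choose.

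**The case against.** *The documents define no follower-level status.* True. The rule of no answered Tweet is supplied here, and the Section 1 definition is an aside about earlier work. The caption of Figure 1 in Section 3 says account pairs feed the network analyses, so an isolate could be an account with no ties. That status would be binary without collapsing Tweets, and (1 − q)^m would not describe it. But the plan does not say so, and that reading conflicts with its own definition. The gap between unit and test remains.

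*A reader might infer that McNemar's test here simply measures how often followers post.* The documents do not support that. Even under the assumed rule, status depends on both posting and response rate. It is confounded by posting, not a measure of it.

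*A reader might infer that posting alone reproduces the planned effect.* No effect is planned for this test. The 0.1525 in Section 2 belongs to the Black–Hispanic comparison in Hypothesis 2.

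*A reader might infer that the sign flips freely with the rule.* It flips at low posting, but negligibly at 10 to 15 Tweets.

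*The intervention also acts on the answer rate, and having fewer caregivers with no response is a fair person-level aim.* Both points stand. They support keeping a follower-level result as secondary, described for what it is.

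*PROC GLIMMIX is already listed.* The plan chooses it according to missing data. Fitted to the same follower status, it carries the same confounding.

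**Conclusion.** The concern holds in a limited form. The stated test does not fit the outcome as the plan defines it, and the step linking them is missing. If that step is the rule of no answered Tweet, a rise in posting can yield a significant fall in isolates at an unchanged answer rate. For a 1.5-fold rise, q of 5% to 10%, 160 followers and independent windows, rejection is about 23–40% at 2 to 3 Tweets and about 68–82% at 10 to 15, against a nominal 5%.

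These sizes rest on assumed answer and posting rates and on a rule the plan has not adopted. They show what could happen, not what will. As written, a significant Hypothesis 1 result on isolates could not be read as improved support.

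**What to change.** - State the unit and definition of an isolate, and how followers with no Tweets in a window are handled.
- Make the main Hypothesis 1 isolate analysis the proportion of unanswered Tweets per follower and window. Use PROC GLIMMIX in events/trials form (unanswered over written), with a random follower effect plus a follower-by-window (overdispersion) term or robust standard errors, and test the period term. A paired test on follower proportions is a simpler alternative. The extra term matters: in a simulation using a conditional test in place of GLIMMIX, ignoring follower-by-window variation gave 9–20% false rejection.
- Report Tweets per follower, and the number of followers with no Tweets in a window, as separate outcomes.
- Keep any follower-level McNemar result as secondary, described as reflecting both posting and response.
- Withdraw the 208, or restate it with its inputs for the chosen analysis.

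The cost is analysis-plan wording and one recalculated sample size. The Section 3 daily collection of user IDs, relationships, Tweets and time stamps already covers both windows. The downside is that followers with no Tweets in a window, arguably the most isolated, add nothing to the per-Tweet comparison for that window. That is why their number must be reported alongside it.
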